### 2.11.2 Immune cells and MM

An important step in the progression of tumors is evasion and suppression of the host immune system. Several numerical and functional T cell abnormalities have been reported in MM. Studies have shown an increase of functional T-reg in MM patients and MM mouse models, which may lead to suppression of immune effector cells. It was also reported that T-reg increase during progression in MM, and increased number of T-reg are associated with survival. Since, there are some conflicting data and lack of good murine myeloma models for analyzing immune cells, the significance of T-reg and other immune cells in MM pathogenesis is not fully understood. Myeloid-derived suppressor cells (MDSCs) are a heterogeneous, immature myeloid cell population with the ability to suppress immune responses. Recent studies have shown that MDSCs induce MM growth while suppressing T-cell-mediated immune responses. SLAMF7 is highly expressed on NK cells. Accumulating evidence indicates that EAT-2 mediates its activating effect on NK cells via tyrosine 127 which is believed to undergo phosphorylation on engagement of SLAMF7. Elotuzumab may interfere with the ability of myeloid derived suppressor cells (MDSC's) to suppress anti-myeloma immune responses by T cells or other immune cells. In mice it has been demonstrated that engagement of SLAMF7 on T helper cells inhibited antigen induced T cell proliferation and cytokine production, indicating that SLAMF7 may be inhibitory in T-cells however this would depend on the presence or absence of EAT2. Therefore the characterization of SLAMF7, EAT2 and elotuzumab treatment on T cell subsets remains an unanswered question in MM and may help to unravel the mechanism of synergy between elotuzumab and lenalidomide. Based on these studies and based on the SLAMF7 role in these cells, we will focus our studies of immune regulation on 3 types of cells: NK cells, T-reg and MDSCs.

## 3. PARTICIPANT SELECTION

### 3.1 Eligibility Criteria

3.1.1 Age  $\geq$  18 years.

3.1.2 Must meet criteria of high risk smoldering MM as described with one of the below criteria:

- Bone marrow clonal plasma cells  $\geq$ 10% and any one or more of the following:
  - Serum M protein  $\geq$ 3.0 gm/dL
  - IgA SMM
  - Immunoparesis with reduction of two uninvolved immunoglobulin isotypes
  - Serum involved/uninvolved free light chain ratio  $\geq$ 8 (but less than 100)
    - *Free Light Chain Smoldering Myeloma patients as defined in section 2.4 are not excluded*
  - Progressive increase in M protein level (Evolving type of SMM)†
  - Bone marrow clonal plasma cells 50-60%
  - Abnormal plasma cell immunophenotype ( $\geq$ 95% of bone marrow plasma cells are clonal) and reduction of one or more uninvolved

CONFIDENTIAL

This document is confidential. Do not disclose or use except as authorized.

immunoglobulin isotypes

*\* All patients should have four or six color flow cytometry performed on the baseline bone marrow sample, as feasible. Patients evaluated for eligibility by Spanish Criteria must have their result confirmed by four color flow cytometry. If four or six color flow cytometry is not available at the site, the baseline bone marrow must be sent to Dana-Farber Cancer Institute to confirm eligibility prior to enrollment.*

- t (4;14) or del 17p or 1q gain
- Increased circulating plasma cells
- MRI with diffuse abnormalities or 1 focal lesion ( $\geq 5\text{mm}$ )
- PET-CT with one focal lesion ( $\geq 5\text{mm}$ ) with increased uptake without underlying osteolytic bone destruction

*† Increase in serum monoclonal protein by  $\geq 10\%$  on two successive evaluations within a 6 month period*

3.1.3 No evidence of CRAB criteria\* or new criteria of active MM which including the following:

- Increased calcium levels: Corrected serum calcium  $>0.25\text{ mmol/L}$  ( $>1\text{mg/dL}$ ) above the upper limit of normal or  $>2.75\text{ mmol/L}$  ( $>11\text{mg/dL}$ );
- Renal insufficiency (attributable to myeloma);
- Anemia (Hgb 2g/dL below the lower limit of normal or  $<10\text{g/dL}$ );
- Bone lesions (lytic lesions or generalized osteoporosis with compression fractures)
- No evidence of the following new criteria for active MM including the following: Bone marrow plasma cells  $>60\%$ , Serum involved/uninvolved FLC ratio  $\geq 100$ , and MRI with more than one focal lesion

*\* Participants with CRAB criteria that are attributable to conditions other than the disease under study may be eligible*

3.1.4 ECOG Performance Status (PS) 0, 1, or 2 (Appendix A)

3.1.5 The following laboratory values obtained  $\leq 21$  days prior to registration:

- ANC  $\geq 1000/\mu\text{L}$
- PLT  $\geq 50,000/\mu\text{L}$
- Total bilirubin  $\leq 2.0\text{ mg/dL}$  (If total is elevated check direct and if normal patient is eligible.)
- AST  $\leq 3 \times$  institutional upper limit of normal (ULN)
- ALT  $\leq 3 \times$  institutional upper limit of normal (ULN)
- Estimated creatinine clearance  $\geq 60\text{mL/min}$  or a creatinine  $\leq 2.2\text{ mg/dL}$

3.1.6 Voluntary written informed consent before performance of any study-related procedure not part of normal medical care, with the understanding that consent may be withdrawn by the subject at any time without prejudice to future medical care.

CONFIDENTIAL

This document is confidential. Do not disclose or use except as authorized.

3.1.7 Females of childbearing potential\* must have a negative serum or urine pregnancy test with a sensitivity of at least 50 mIU/mL within 10 – 14 days and again within 24 hours prior to prescribing lenalidomide for Cycle 1 (prescriptions must be filled within 7 days as required by Revlimid REMS®) and must either commit to continued abstinence from heterosexual intercourse or begin TWO acceptable methods of birth control, one highly effective method and one additional effective method AT THE SAME TIME, at least 28 days before she starts taking lenalidomide.

\* *A female of childbearing potential is a sexually mature female who:*

- *has not undergone a hysterectomy (the surgical removal of the uterus) or bilateral oophorectomy (the surgical removal of both ovaries) or*
- *has not been naturally postmenopausal (amenorrhea following cancer therapy does not rule out childbearing potential) for at least 24 consecutive months (i.e., has had menses at any time during the preceding 24 consecutive months)*

3.1.8 All study participants must be registered into the mandatory Revlimid REMS® program, and be willing and able to comply with the requirements of the REMS® program.

3.1.9 Females of reproductive potential must adhere to the scheduled pregnancy testing as required in the Revlimid REMS® program.

3.1.10 Men must agree to use a latex condom during sexual contact with a female of childbearing potential even if they have had a successful vasectomy.

3.1.11 Ability to understand and the willingness to sign a written informed consent.

## 3.2 Exclusion Criteria

3.2.1 Symptomatic Multiple Myeloma or any evidence of CRAB criteria including the new criteria for overt myeloma. Any prior therapy for active Myeloma should also be excluded. Prior therapy for smoldering myeloma is not an exclusion criterion. Bisphosphonates are not excluded

3.2.2 Other concurrent chemotherapy, immunotherapy, radiotherapy, or any ancillary therapy considered investigational. Prior therapy with bisphosphonate is allowed. Prior radiation therapy to a solitary plasmacytoma is allowed. Prior clinical trials or therapy for smoldering MM or MGUS are allowed but should be discussed with the Principal Investigator.

3.2.3 Serious medical or psychiatric illness likely to interfere with participation in this clinical study.

CONFIDENTIAL

This document is confidential. Do not disclose or use except as authorized.

- 3.2.4 Diagnosed or treated for another malignancy within 2 years of enrollment, with the exception of complete resection of basal cell carcinoma or squamous cell carcinoma of the skin, an in situ malignancy, or low-risk prostate cancer after curative therapy.
- 3.2.5 Uncontrolled intercurrent illness including, but not limited to, ongoing or active infection, symptomatic congestive heart failure, unstable angina pectoris, cardiac arrhythmia, or psychiatric illness/social situations that would limit compliance with study requirements.
- 3.2.6 Pregnant or nursing women will be excluded from the study because lenalidomide is an agent with the potential for teratogenic or abortifacient effects.
- 3.2.7 History of allergic reactions attributed to compounds of similar chemical or biologic composition to elotuzumab or lenalidomide.
- 3.2.8 Known seropositive for or active viral infection with human immunodeficiency virus (HIV), hepatitis B virus (HBV) or hepatitis C virus (HCV). Patients who are seropositive because of hepatitis B virus vaccine are eligible. Patients who are positive for hepatitis B core antibody or hepatitis B surface antigen must have a negative polymerase chain reaction (PCR) result before enrollment. Those who are PCR positive will be excluded.

### **3.3 Inclusion of Women and Minorities**

- 3.3.1 Both men and women of all races and ethnic groups are eligible for this trial.

## **4. REGISTRATION PROCEDURES**

### **4.1 General Guidelines for DF/HCC and DF/PCC Institutions**

Institutions will register eligible participants in the Clinical Trials Management System (CTMS) OnCore. Registrations must occur prior to the initiation of protocol therapy. Any participant not registered to the protocol before protocol therapy begins will be considered ineligible and registration will be denied.

An investigator will confirm eligibility criteria and a member of the study team will complete the protocol-specific eligibility checklist.

Following registration, participants may begin protocol therapy. Issues that would cause treatment delays should be discussed with the Overall Principal Investigator (PI). If a participant does not receive protocol therapy following registration, the participant's registration on the study must be canceled. Registration cancellations must be made in OnCore as soon as possible

### **4.2 Registration Process for DF/HCC and DF/PCC Institutions**

CONFIDENTIAL

This document is confidential. Do not disclose or use except as authorized.

DF/HCC Standard Operating Procedure for Human Subject Research Titled *Subject Protocol Registration* (SOP #: REGIST-101) must be followed.

#### 4.3 General Guidelines for Other Investigative Sites

Eligible participants will be entered on study centrally at DFCI by the Study Coordinator. All sites should call the Research Project Manager, at the lead site.

Following registration, participants should begin protocol therapy as soon as possible. Issues that would cause treatment delays should be discussed with the Overall PI. If a participant does not receive protocol therapy following registration, the participant's registration on the study must be canceled. The lead study team should be notified of cancellations as soon as possible.

#### 4.4 Registration Process for Other Investigative Sites

To register a participant, the following documents should be completed by the research nurse or data manager and e-mailed to the Research Project Manager:

- Copy of labs and clinical information that satisfy inclusion criteria
- Signed participant consent form
- HIPAA authorization form
- Registration Form
- Completed eligibility checklist

The research nurse or data manager at the participating site will then call or e-mail the Research Project Manager to verify eligibility. To complete the registration process, the Research Project Manager will follow DF/HCC Standard Operating Procedure for Human Subject Research titled *Subject Protocol Registration* (SOP# REGIST-101) and register the participant on the protocol. The lead site will then fax or email the participant study number to confirm registration.

**Treatment may not begin without confirmation from the Coordinating Center that the participant has been registered.**

**NOTE: Registration and randomization can only be conducted during the business hours of 8:00 AM and 5:00 PM Eastern Time Monday through Friday.** Same day treatment registrations will only be accepted with prior notice and discussion with the DF/HCC.

### 5. TREATMENT PLAN

#### 5.1 Treatment Regimen

All patients will be treated with elotuzumab, lenalidomide and dexamethasone. Patients will also be stratified by age >65 years or older and high risk cytogenetics based on t(4:14), t(14:16), 17p deletion or p53 mutation, +1q amplification.

A treatment cycle is defined as 28 consecutive days.

CONFIDENTIAL

This document is confidential. Do not disclose or use except as authorized.

Elotuzumab will be administered Cycles 1 and 2 on days 1, 8, 15, 22 and cycles 3-8 on days 1 and 15. Lenalidomide will be administered days 1-21 every 28 days. Dexamethasone will be administered on days 1, 8, 15 and 22 on cycles 1-2 then on days 1, 8 and 15 on cycles 3-8. Patients on maintenance treatment will be administered elotuzumab on day 1, and lenalidomide on days 1-21. For treatment cycles 1 and 2, a +/- 3 day window is allowed.

For treatment cycle 3-24, a +/- 7 day window is allowed. Treatment will be administered on an *outpatient* basis.

Reported adverse events and potential risks are described in Section 7. Appropriate dose modifications are described in Section 6. No investigational or commercial agents or therapies other than those described below may be administered with the intent to treat the participant's malignancy.

The participant will be requested to maintain a medication diary of each dose of lenalidomide and dexamethasone. The medication diary should be returned to clinic staff at the end of each cycle.

Elotuzumab and Lenalidomide Dexamethasone Combination (Cycles 1-2)					
Agent	Premedication and Precautions	Schedule	Dose	Route	Cycle Length
Elotuzumab	Premedications are described below	Days 1, 8, 15, 22	10 mg/kg	Intravenous-See appendix B for more details	28 days (4 weeks)
Lenalidomide	None	Days 1-21 of each cycle	25 mg	Oral	
Dexamethasone	Take with food; recommended to be taken in the morning	Days 1, 8, 15, 22	8 mg	IV	
			32 mg	Oral	

CONFIDENTIAL

This document is confidential. Do not disclose or use except as authorized.

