Dosing Regimen	Each Cycle = 28 days Cycle 1 & 2 

Elotuzumab (IV): Days 1, 8, 15 ,22

Lenalidomide (oral): Day 1-21

CONFIDENTIAL

This document is confidential. Do not disclose or use except as authorized.

	

• Dexamethasone: (oral and IV): Days 1, 8, 15, 22

 
Cycles 3-8
 

• Elotuzumab (IV): Days 1 and 15

• Lenalidomide (oral): Day 1-21

• Dexamethasone: (oral and IV): Days 1, 8, 15

 
Cycles 9-24 (maintenance)
 

• Elotuzumab (IV): Days 1

• Lenalidomide (oral): Day 1-21

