**Elotuzumab and Lenalidomide Maintenance Therapy (Cycles 9-24)**

Agent	Premedication and Precautions	Schedule	Dose	Route	Cycle Length
Elotuzumab	Premedications are described below	Days 1 of each cycle	20 mg/kg	Intravenous-See appendix B for more details	
Lenalidomide	None	Days 1-21 of each cycle	15 mg	Oral	28 days (4 weeks)
Dexamethasone*	Take with food; recommended to be taken in the morning	Day 1 of each cycle	8 mg	IV	
			28 mg	Oral	

\* After discussion with the overall PI, high-dose dexamethasone may be re-added during maintenance due to biochemical progression (progressive increase in SPEP [25% and an absolute increase of 0.5g/d] or UPEP [25% and an absolute increase of 200mg/24hours] on 2 successive evaluations as determined by the IMWG response criteria or documented progression by the FreeLite™ progressive disease criteria in the absence of serum or urine involvement). Dexamethasone should be given as follows after overall PI approval:

Day	Dose	Route
1	8 mg	IV
	32 mg	Oral
8	40 mg	Oral
15	40 mg	Oral

CONFIDENTIAL

This document is confidential. Do not disclose or use except as authorized.

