### 5.2.1 Premedication Regimen in Subjects without a Prior Infusion Reaction

- Premedication is required prior to all Elotuzumab infusions. Refer to table 3 for the guidelines for premedication.

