**Table 3: Recommended Corticosteroid Premedication**

None or Grade 1 Prior Infusion Reaction	24-3 hours prior to Elotuzumab Infusion	32 mg PO Dexamethasone
	90-45 min prior to Elotuzumab Infusion	8mg IV Dexamethasone Diphenhydramine 25-50 mg IV or PO or equivalent H1 blocker Ranitidine 50mg IV or equivalent H2 blocker Acetaminophen 650-1000mg PO
Prior Grade 2 Infusion Reaction	24-3 hours prior to Elotuzumab Infusion	30mg PO Dexamethasone
	90-45 min prior to Elotuzumab	10mg IV Dexamethasone Diphenhydramine 50 mg IV or PO or equivalent H1 blocker Ranitidine 50mg IV or equivalent H2 blocker Acetaminophen 1000mg PO
Prior Grade 3 Infusion Reaction or recurrent Grade 2	24-12 hours prior to Elotuzumab Infusion	8mg PO Dexamethasone
	No more than 3 hours prior to Elotuzumab Infusion	14mg PO Dexamethasone
	90-45min prior to Elotuzumab	18mg IV Dexamethasone Diphenhydramine 50 mg IV or PO or equivalent H1 blocker Ranitidine 50mg IV or equivalent H2 blocker Acetaminophen 1000mg PO

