### 8.3.7 Administration

, Participants will receive dexamethasone Days 1, 8 15 and 22 during cycles 1-2 and then days 1, 8, 15 on cycles 3-8 and on day 1 of cycles 9-24 of maintenance .

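### Maintenance dexamethasone (cycles 9-24) is specified inconsistently: left out of the Synopsis and the 5.1 text, 36 mg on Day 1 in the 5.1 table, 40 mg under Table 3

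*Combined protocol and SAP*

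**What the plan says.** All references are to the combined protocol and SAP.

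- **Synopsis, dosing regimen.** Dexamethasone is listed for cycles 1-2 and 3-8. Under "Cycles 9-24 (maintenance)" only elotuzumab and lenalidomide appear.
- **Section 5.1, text.** It opens with "All patients will be treated with elotuzumab, lenalidomide and dexamethasone", gives dexamethasone days for cycles 1-8 only, and then states "Patients on maintenance treatment will be administered elotuzumab on day 1, and lenalidomide on days 1-21".
- **Section 5.1, maintenance table.** The title, "Elotuzumab and Lenalidomide Maintenance Therapy (Cycles 9-24)", does not mention dexamethasone, but a row gives it on Day 1 of each cycle as 8 mg IV and 28 mg oral. The footnote says that, after discussion with the overall PI, "high-dose dexamethasone may be re-added during maintenance due to biochemical progression". The Day 1 dose of that re-added schedule is 8 mg IV plus 32 mg oral.
- **Section 5.2.1 and Table 3.** "Premedication is required prior to all Elotuzumab infusions", following Table 3. For no or a Grade 1 prior reaction, Table 3 gives "32 mg PO Dexamethasone" plus 8 mg IV. It has no maintenance row or exception.
- **Section 5.2.2.** After a Grade 2 reaction the IV dose is 10 mg; after Grade 3 or recurrent Grade 2 it is 18 mg. The premedication for the reaction's severity then applies for the rest of the trial.
- **Section 5.3.3.** It points to Table 3 for giving oral dexamethasone and to section 5.1 for dosing.
- **Sections 6.1 and 6.3.** Both tie dexamethasone to every elotuzumab infusion.
- **Table 5 and section 8.3.7.** The Table 5 footnotes limit maintenance dexamethasone to Day 1. Section 8.3.7 lists it "and on day 1 of cycles 9-24 of maintenance", with no dose.

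**The concern.** Cycles 9-24 are 16 of the 24 planned cycles, and the passages a site would consult for Day 1 of those cycles do not agree. Section 5.3.3 sends the reader to two sources that give different oral doses in maintenance, and no rule says which prevails. In a multi-center trial, sites can follow different passages in good faith.

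Three things are at stake. First, the steroid part of the tested regimen cannot be described in one way for two-thirds of the planned cycles. Second, a site that follows one passage departs from another, so deviations cannot be classified consistently. Third, for patients with an earlier infusion reaction, the maintenance table and the reaction-specific premedication rules disagree on the IV dose given before the infusion.

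**Working it through.** No power or sample size figure is involved. The check sets the passages side by side and adds the IV and oral components.

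**Step 1. Is dexamethasone part of maintenance?** The Synopsis and the 5.1 text leave it out. The 5.1 maintenance table, sections 6.1, 6.3 and 8.3.7, and the Table 5 footnotes put it in. The omission is a conflict with these passages, not an instruction to withhold.

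**Step 2. Day 1 dose by source (mg).**

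| Source | IV | Oral | Total |
|---|---|---|---|
| 5.1 maintenance table, all patients | 8 | 28 | 36 |
| Table 3, no or Grade 1 prior reaction | 8 | 32 | 40 |
| Table 3 and 5.2.2, prior Grade 2 | 10 | 30 | 40 |
| Table 3 and 5.2.2, prior Grade 3 or recurrent Grade 2 | 18 | 8 + 14 = 22 | 40 |
| 5.1 footnote, re-added schedule, Day 1 | 8 | 32 | 40 |

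**Step 3. Size for patients with no or a Grade 1 prior reaction.** The IV dose agrees. The oral gap is 32 - 28 = 4 mg, and 4/40 = 10% of the Table 3 total. Maintenance has 24 - 9 + 1 = 16 cycles, so the cumulative doses are 16 × 36 = 576 mg and 16 × 40 = 640 mg, a difference of 64 mg. This assumes all 16 cycles are given with no reduction.

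**Step 4. Patients with prior reactions.** The total differs by the same 4 mg, but the split differs more. After Grade 2 the IV gap is 10 - 8 = 2 mg. After Grade 3 or recurrent Grade 2 it is 18 - 8 = 10 mg, and the oral dose differs the other way (28 against 22 mg). The maintenance table makes no distinction by prior reaction.

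**Step 5. The footnote against Table 3.** The footnote allows its high-dose schedule in maintenance only for biochemical progression and with overall PI approval. The Day 1 dose of that schedule, 8 + 32 = 40 mg, is what Table 3 gives routinely before any elotuzumab infusion. The schedules differ on Days 8 and 15, where the footnote adds 40 mg oral each, but their Day 1 doses are the same.

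**Step 6. Dose reduction.** In Table 5 (no or Grade 1 reaction, week with elotuzumab) the starting level is 32 + 8 = 40 mg, the first reduction is 28 + 8 = 36 mg and the second is also 28 + 8 = 36 mg. The 5.1 maintenance dose of 36 mg therefore equals both reduction levels. Section 6.3 asks for a one-level reduction after certain toxicities. A patient already on 36 mg, with Day 1 the only dexamethasone day, would go from 36 to 36 mg; a patient counted as on 40 mg would go to 36 mg.

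**The case against.** The strongest reply is that the 5.1 maintenance table is specific to cycles 9-24 and gives a day, dose and route, whereas Table 3 is a general table of recommended premedication. On that view the specific table governs, section 5.3.3 confirms this by pointing to 5.1 for dosing, and the footnote shows that the authors separated a routine 36 mg from a high-dose schedule. What remains would be a 4 mg oral difference and some loose cross-references.

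Much of this stands. A reader might infer from the conflict that the cycles 9-24 regimen is undefined; it is not, because the table does define one. A reader might also infer from the Synopsis and the 5.1 text that 0 mg is a live option. The documents do not support that: sections 6.1 and 6.3 require dexamethasone with every elotuzumab infusion, and section 8.3.7 and the Table 5 footnotes place it on Day 1. Nor do the documents show that a 4 mg oral difference would by itself harm patients.

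The reply does not remove the conflict. No passage says that the maintenance table overrides Table 3. Section 5.2.1 extends Table 3 to all infusions, and section 5.3.3 cites both sources. For patients with earlier reactions, section 5.2.2 expressly continues the severity-specific premedication through the trial, which the maintenance table does not accommodate. The overlap with the Table 5 reduction levels also remains.

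**Conclusion.** The point holds as an internal inconsistency. For patients with no or a Grade 1 prior reaction, the documents support two Day 1 totals, 36 and 40 mg. For patients with a prior Grade 2, or Grade 3 or recurrent Grade 2, reaction, the IV dose conflicts as well: 8 mg against 10 or 18 mg. The cumulative figures in the working are upper limits on the divergence between the two sources for a patient who completes maintenance unreduced; patients who stop early or reduce would diverge less.

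The conclusion rests on reading the requirement to premedicate before all infusions as including cycles 9-24, which its wording does. It takes no position on which dose is right. It does not reach the primary analysis: the 39-patient design and the threshold of 24 progression-free patients in section 13.1 do not depend on the dexamethasone dose. It should be corrected because it bears on premedication, dose-reduction handling and the description of the regimen in 16 of 24 cycles.

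**What to change.** The sponsor should reconcile the Synopsis dosing regimen, the 5.1 text, the 5.1 maintenance table and its footnote, section 5.2.2, Table 3, section 5.3.3, Table 5 and section 8.3.7, so that:

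1. one maintenance dexamethasone schedule is stated wherever the regimen is described;
2. that schedule covers patients with prior infusion reactions of each severity;
3. the starting level for dose reductions in maintenance is identified, so that a one-level reduction has a defined meaning;
4. one passage is named as governing if any difference remains.

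The choice of dose is a clinical decision for the sponsor. The cost is a wording amendment with the usual IRB review at the sites. It needs no new data and no change to the sample size, endpoint or decision rule.
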